assessment includes behavioral health issues (e.g., smoking, weight management), 6) inter-professional communication at each encounter (determined by PCP and co-locate MHPs co-signing notes), 7) co-located MHPs use motivational interviewing, self-management, problem solving therapy, cognitive techniques, and brief alcohol interventions, and 8) symptom severity is measured using structured assessments (e.g., PHQ9).

Dependent Variable for Implementation Fidelity: Fidelity will be measured as a percentage: with the numerator specified as the number of documented clinical activities and the denominator specified as the number of clinical activities relevant to that patient. For example, medication adherence and side-effect assessments will only be specified in the denominator if the patient has been prescribed medications.

Data Analysis for Implementation Fidelity: - The mean, median, standard deviation and range of implementation fidelity will be reported for all Veterans enrolled during the intervention phase, as well as the sub-sample with a PC-MHI (534) stopcode. The fidelity measures will also be aggregated at the CBOC level.

Interview Assessment Data: We will administer research assessments to those Veterans providing informed consent to participate in the primary data collection efforts associated with the trial. The baseline assessment will be conducted within two weeks following the regularly scheduled PC appointment and six months afterwards. Assessments will be administered over the phone by trained RAs using a CATI system. Table 3 lists the instruments and Appendix 5 contains the actual survey items to be used in the baseline interview. The demographics section, barriers assessment, perceived access inventory, and readiness ruler will only be administered at baseline and used for casemix adjustment. All other instruments will be administered at both baseline and follow-up. The rurality of Veterans will be measured based on their self-reported zipcode using the methods described above.

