Dependent Variable for Effectiveness (Hypothesis 2): Change scores between baseline and six months will be calculated for non-disease specific outcomes including: MH status (SF12V MCS), physical health status (SF12V PCS), pain (Pain scale), sleep (Jenkins sleep scale), disease specific symptoms such as depression (PHQ9), general anxiety disorder (GAD7), panic disorder (PDSS-SR), PTSD (PCL-5) and alcohol use (AUDIT-C), and self-management of chronic disorders such as diet and exercise (Prime-Screen), smoking (BRFS tobacco use items) and medication adherence (Miklowitz adherence scale). The primary outcome for this hypothesis is the MCS from the SF12V. The other outcome domains will be examined in exploratory analyses. Exploratory analysis will also examine the variation in SF12V and disease specific outcomes across diagnostic categories (identified by baseline scores of the PHQ9, GAD7, PDSS-SR, PCL-5, and AUDIT-C).

Table 3 - Research Assessments

Instrument	Construct
Socio-Demographics	18 items that measure socio-economic and military characteristics
Hoge Barriers Assessment	14 item measure of perceived access, need and treatment effectiveness ⁵⁹
Perceived Access Inventory	43 item perceived access instrument developed by CREATE Project 1
Readiness Ruler	3 items that assess perceived readiness to seek treatment ⁶⁰
Miklowitz-Adherence Scale	2 item medication adherence scale ⁶¹
SF12V	12 items addressing overall physical and mental health functioning ⁶²

Pain Scale	Single item participant rating of the average overall level of pain for the past week rated on a continuous scale from 0 to 10.
Jenkins Sleep Scale	4 item measure that assesses trouble falling and staying asleep, and feeling tired during the daytime ⁶³
Prime-Screen	6 item assessment of dietary and exercise habits/behaviors ⁶⁴
PHQ9	9 item inventory that yields a continuous and dichotomous assessment of depression ⁶⁵
GAD7	7 item inventory that yields a continuous and dichotomous assessment of generalized anxiety disorder ⁶⁶
APA DSM 5 Severity Measure for Panic- Adult	10 item inventory that yields a continuous and dichotomous assessment of panic disorder ⁶⁷
PCL-5	20 item inventory that yields a continuous and dichotomous assessment of PTSD ⁶⁸
AUDIT-C	3 items that yield a continuous and dichotomous assessment of alcohol use ⁶⁹
BRFSS Tobacco Use	5 items to assess current tobacco use

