CBOCs are the unit of randomization, with CBOCs randomized to an intervention start date using the stepped wedge design. A total of 6 CBOCs will participate in the study, with two CBOCs allocated to each of the 3 start dates. Randomization will be computer-generated by the statistician. A subset of potential patients (based on inclusion criteria) will be selected at each CBOC on a daily basis during the 5 measurement periods shown in Figure 1: Grant Activity Timeline (the formative evaluation control period(s), implementation, and step down period(s)).

Blinding

CBOCs and the research team will not be blinded to the intervention start dates. However, outcome assessment by independent evaluators (research assistants) will be blinded.

Statistical Analysis

The analyses will be conducted using the intention-to-treat principle, with CBOCs analyzed according to their randomized, crossover time irrespective of whether crossover took place at

the specified time. The results across the unexposed (control phase) observation periods will be compared with those across the observation periods in which the CBOCs are exposed to the Telemedicine Blended Model intervention (intervention phase). Characteristics of the patients and the CBOCs will be summarized by exposure status to examine potential selection bias or lack of balance.⁸¹ Because we have a small number (3) of randomization steps, we will compare numbers of patients analyzed, cluster (CBOC) size, CBOC characteristics and patient characteristics by randomization group. Patient-level data will be collected, with the primary analysis being patient-level.

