The CBOC-level analysis will examine the primary and secondary outcomes, summarized as the mean and standard deviation across CBOCs before and after implementation of Telemedicine Based care. At each facility, we will determine the index start date at which the first utilization of the telemedicine based service began. This will allow us to take into account the differing lengths of time it may take to implement the intervention at various CBOCs. Before this index date, patients participating in the study at that CBOC will be considered as being in the control period and those participating after the index date will be considered in the intervention phase. Analyses of before to after implementation will be conducted for continuous outcomes using linear mixed models. The interaction of intervention by CBOC will test if results differ by CBOC. We will adjust for baseline differences among CBOCs in the model.⁸²

The patient-level analysis will be a generalized linear mixed model (GLMM) which includes fixed terms for intervention (usual care referral model versus Telemedicine Based care) and time (6-month time periods for each step). The model will use random effects to model the correlation of patients within CBOCs.

The random effects model is:

$$Y_{ijl} = \mu + \beta_j + X_{ij}\theta + u_i + \varepsilon_{ijl} ; \\ u_i \sim N(0, \sigma^2_b) , \varepsilon_{ijl} \sim N(0, \sigma^2_w)$$

where β_j = fixed effect of time; $X_{ij} = 1$ if intervention, 0 otherwise; θ = intervention effect; u_i = random effect for cluster i ; ε_{ijl} = residual; $i = 1, 2, \dots, k$ clusters; $j = 1, 2, \dots, T$ time periods; and $l = 1, 2, \dots, m$ individuals.^{83, 84} In addition, we may consider adjusting the analyses to deal with lags in the intervention effect. This delayed intervention effect occurs if the intervention does not become fully effective during the step in which it is introduced.⁸⁵ If, for example, we expect the lag in the intervention effect to be 50% in the implementation step and 100% effective within 6 months, we could follow the suggestion of Hussey and Hughes of using fractional values for the treatment indicator.⁸³

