In our study, the 6 CBOCs will be randomly allocated two at a time to one of the $t = 3$ randomization steps. Based on earlier work, the intracluster correlation coefficient, ρ will be estimated as .01. There will be a total of 5 measurements for each cluster, including the control period(s), implementation, and maintenance period(s) (see schematic diagram). We assumed for the power calculations that approximately $m=18$ participants would be available within each CBOC in each 6-month time interval.

The calculations are based on having 80% power at a significance level of 0.05 to detect a medium effect size (Cohen's $d=0.42$) between the usual care referral model (EU) and the Telemedicine Blended model intervention group (TB) in our primary outcome measure for the effectiveness hypothesis, MCS from SF-12V. This represents a difference of 4 points in the MCS scores between the referral model group and the Telemedicine Blended Model group, assuming a pooled standard deviation of 10. This gives the unadjusted total sample size, N_u , of 128 for the two-sided, two-sample t-test of equal means.

The total number of patients to be selected for assessment across the 6 CBOCs will be 750. This was determined after adjusting the total sample size required under individual randomization N_u , for the design effect, multiplying by the 5 measurement periods, and accounting for a 20% attrition rate. This will result in approximately 600 patients providing baseline and 6-month follow-up data for analysis, accounting for attrition.

The assumption of approximately 18-30 participants at each CBOC in each 6-month period does not represent the maximum that can be recruited at a site in any six-month period; it is a possible average based on our experience in the first six-months of recruitment. We will recruit all eligible participants at the study sites as described elsewhere in the protocol.

Direct Access to Source Data/Documents:

Only authorized persons will have access to the information gathered in this study. Authorized persons may include regulatory agencies such as, the Government Accounting Office (GAO) or the Office for Human Research Protection (OHRP), Office of Research Oversight (ORO), as well as members of the Research Administration staff of CAVHS.

Data Safety and Monitoring Plan:

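### The primary patient-level model for six-month MCS change would be more precise with each patient's baseline MCS as a covariate; the score is already collected, but the plan does not put it in the model

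*Combined protocol and SAP*

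**What the plan says.** The section on the dependent variable for Effectiveness makes the SF12V MCS the primary outcome and analyses it as change: "Change scores between baseline and six months will be calculated for non-disease specific outcomes including: MH status (SF12V MCS".

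Under Statistical Analysis, "Patient-level data will be collected, with the primary analysis being patient-level". The patient-level model there is described as having "fixed terms for intervention (usual care referral model versus Telemedicine Based care) and time (6-month time periods for each step"; clustering is handled by a CBOC random effect. The printed equation has a mean, a period effect, the intervention effect, a CBOC random intercept and a residual.

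Four statements come close to baseline adjustment:

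- Interview Assessment Data: "The demographics section, barriers assessment, perceived access inventory, and readiness ruler will only be administered at baseline and used for casemix adjustment". The SF12V is not in that group. It falls under the next sentence: "All other instruments will be administered at both baseline and follow-up".
- Statistical Analysis, in the paragraph on the CBOC-level analysis: "We will adjust for baseline differences among CBOCs in the model".
- Statistical Analysis, on balance: "Characteristics of the patients and the CBOCs will be summarized by exposure status to examine potential selection bias or lack of balance".
- Data Analysis for Reach lists casemix factors, but for the Hypothesis 1 model.

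None of them names the patient's own baseline MCS as a term in the Hypothesis 2 patient-level model.

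**The concern.** Subtracting baseline from the six-month score is the same as adjusting for baseline with a slope forced to 1. If the true slope is below 1, the subtraction adds noise. The slope is r × SD6/SD0, where SD0 and SD6 are the SDs at baseline and six months. Estimating it removes that noise.

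The study has six clusters and is sized for 80% power with little margin, so wasted precision in the primary estimate matters. The covariate must already exist for every patient who has a change score. Summarising characteristics by exposure shows imbalance but does not correct the estimate for it. Correcting chance imbalance in baseline MCS is the same gain as the lower variance, not a second one.

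**Working it through.** **Inputs from the documents** (Power Calculation for Hypothesis 2): two-sided alpha 0.05, 80% power, d = 0.42, 4 MCS points, SD 10, ICC 0.01, t = 3 steps, T = 5 periods, 6 CBOCs, m = 18, 20% attrition, 750 enrolled, about 600 analysed. The plan gives both 4 points and d = 0.42 (4.2 points at SD 10), so both effects are carried. It does not say whether SD 10 refers to the score or to the change.

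**Assumed, because not given:** r = 0.3, 0.5, 0.7; SD6/SD0 = 1 or 1.2; no credit for casemix covariates.

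**Step 1. The plan's own sample size.** At d = 0.42 the two-sample t-test needs 180 in total. The plan's design effect is 0.6613. Then 180 × 0.6613 × 5 = 595 analysed, and 595/0.8 = 744 enrolled, in line with the stated 600 and 750. The stated intermediate figure of 128 corresponds to d = 0.50 and would give 423 and 529; that is a separate inconsistency. No baseline correlation enters the calculation.

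**Step 2. Standard error under the plan's model.** Generalised least squares for the printed model, with 6 CBOCs, 5 periods, 600/30 = 20 per CBOC-period and ICC 0.01, gives SE 1.478 at SD 10. Crossover at periods 2/3/4 or 3/4/5 gives the same value. The SE scales with the SD of the analysed response. Power = Φ(effect/SE − 1.96).

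**Step 3. Variances.**

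- Change: SD6² + SD0² − 2r·SD6·SD0
- Baseline-adjusted: SD6²(1 − r²)
- Difference: (SD0 − r·SD6)², which is never negative and is zero only when r × SD6/SD0 = 1

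Example with both SDs 10 and r = 0.5: 100 + 100 − 100 = 100 for change; 100 × 0.75 = 75 adjusted; difference (10 − 5)² = 25.

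**Step 4. Power, change analysis vs adjusted analysis.**

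| Case | r | Variance reduction | SE | 4 points | 4.2 points |
|---|---|---|---|---|---|
| (a) SD 10 at both visits | 0.3 | 35% | 1.749 vs 1.410 | 63 vs 81% | 67 vs 85% |
| | 0.5 | 25% | 1.478 vs 1.280 | 77 vs 88% | 81 vs 91% |
| | 0.7 | 15% | 1.145 vs 1.056 | 94 vs 97% | 96 vs 98% |
| (b) SD6 = 10, SD6/SD0 = 1.2 | 0.3 | 24% | 1.616 vs 1.410 | 70 vs 81% | 74 vs 85% |
| | 0.5 | 13% | 1.372 vs 1.280 | 83 vs 88% | 86 vs 91% |
| | 0.7 | 3% | 1.074 vs 1.056 | 96 vs 97% | 97 vs 98% |
| (c) SD of change 10, equal SDs | 0.3 | 35% | 1.478 vs 1.192 | 77 vs 92% | 81 vs 94% |
| | 0.5 | 25% | 1.478 vs 1.280 | 77 vs 88% | 81 vs 91% |
| | 0.7 | 15% | 1.478 vs 1.363 | 77 vs 84% | 81 vs 87% |

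In case (c) the adjusted SD is 10 × √((1 + r)/2).

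**Step 5. Equivalent sample size.** 600 × Var(change)/Var(adjusted) gives the analysed patients an unadjusted analysis would need to match 600 adjusted: 923, 800 and 706 in case (a); 788, 689 and 621 in case (b).

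**Step 6. Sensitivity to the ICC.** Case (a), r = 0.5, 4 points: 83 vs 92% at ICC 0 and 74 vs 85% at ICC 0.05. If the adjusted response had ICC 0.05 while change kept 0.01, case (a) would give 63 vs 78%, 77 vs 85% and 94 vs 95%.

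**The case against.** **The equation may not be the full covariate list.** The baseline-only instruments are assigned to casemix adjustment yet do not appear in the equation either. The sentence on baseline differences among CBOCs could be read broadly, and the reference it cites is not in the list as supplied, so its meaning cannot be checked. What stands: baseline MCS is not named, rather than expressly excluded. That sentence names neither patients nor MCS, and a primary model should not leave this open.

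**The response is inferred.** The equation does not define its outcome, and the power section speaks of a difference in MCS scores. The outcome section does specify change, so the inference is sound.

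**The power stakes are conditional.** This stands. If 10 is the SD of change, power at d = 0.42 is 81% without the covariate. The shortfall to 77% at 4 points comes from the plan's own mismatch between 4 and 4.2 points. The largest gain, 63% to 81%, needs r = 0.3 and SD 10 read as the raw-score SD.

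**Normal critical value with six clusters.** Absolute power is probably optimistic for both analyses. The variance ratio is unaffected.

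**Timing and comparability of baseline.** Baseline is taken up to two weeks after the primary care visit, so in the intervention phase it may follow first contact with the model. The change score uses the same measurement. The precision comparison also assumes no systematic difference in baseline MCS by exposure, which is one reason to keep the unadjusted result alongside.

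**Only an efficiency point.** Agreed: no bias or invalid inference is alleged. It is still worth making, because the change is free and is best named in advance; added later, it could look selective.

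**Conclusion.** The point holds. The plan analyses six-month MCS change without naming the patient's baseline MCS as a covariate, although it is collected. The direction of the gain follows from algebra: at equal ICC, and apart from one parameter, the adjusted estimate is never less precise in expectation. Its size is not known from the documents. Over r = 0.3 to 0.7 the residual variance falls by 15 to 35% with equal SDs and by 3 to 24% with SD6/SD0 = 1.2. Whether this decides if 80% power is reached depends on r, the SD ratio and what the SD of 10 describes. The gain approaches zero as r × SD6/SD0 nears 1, and is smaller if casemix covariates already explain part of baseline MCS. The change score remains a valid analysis.

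**What to change.** In the patient-level model under Statistical Analysis, add the patient's baseline MCS as a fixed covariate in the primary analysis. The response can stay as change in MCS: with baseline in the model, the intervention estimate is the same as for the six-month score. Do likewise for each exploratory continuous scale with its own baseline; the same algebra applies, though no gain has been calculated for those scales. Keep the unadjusted change analysis as a sensitivity analysis.

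The cost is one named covariate in the analysis section. No new data are required, because the SF12V is already given at baseline and follow-up.

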HCV Treatment. New antiviral treatments available in VA can essentially cure HCV. VA continues to fund HCV treatment, including \$500 million last year.³⁶ Less than 30% of HCV+ Veterans have received treatment.³⁷ In a non-systematic literature review, researchers identified barriers to HCV treatment among Veterans and non-Veterans within the health care system (e.g., insufficient funding), patients (e.g., adherence), providers (e.g., referral behavior), and clinical encounters (e.g., communication issues).³⁷ However, no data exist exclusively from Veterans on treatment experiences and barriers or facilitators, especially since the new HCV treatment emerged.

HIV & Depression Treatment. One treatment program exists to improve a condition associated with HIV—depression—and it can improve viral load and reduce depressive symptoms among Veterans³⁸ and is also cost-effective in VA.³⁹ Briefly, the HIV/depression treatment is Care Management for depression in HIV clinics. This model of depression care is preferred by HIV+ Veterans.⁴⁰ However, barriers exist at multiple levels for HIV/depression treatment in VA,⁴⁰ include geographic access to care for rural-dwelling Veterans.⁴¹ There are implementation data of HIV/depression treatment from eight Veterans⁴² and more are needed to reach saturation of themes, especially among vulnerable Veterans.

Exploratory research is needed on racial minority and rural-dwelling populations to identify treatment preferences, barriers, and facilitators to using Care Management and other evidence-based treatments in VA for Hepatitis C, HIV, and comorbid mental health problems.

Known and Potential Risks and Benefits, if any, to Human Participants:

This minimal risk study will consist of participants completing questionnaires about their health care, health status, mental health symptoms, comorbidities and other outcomes, and also of providers, clinical managers and other staff discussing care processes and intervention components. The study will examine the effect of care models that have been endorsed and implemented throughout the VA as compared with usual care in CBOCs. Possible risks for participants are tiredness and boredom; however, the research staff are skilled in conducting assessments and will take all precautions to ensure that any distress is minimized. Loss of confidentiality is also a possible risk; however all information will be treated as confidential and safeguarded in accordance with the Privacy Act of 1974.

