Veterans may benefit from knowing that their participation may be useful to VHA leaders who are seeking to improve mental healthcare and infectious disease care for patients receiving care in CBOCs; however, study participation in itself will not likely result in any direct benefit to participants.

Population to be Studied:

Human Subjects Involvement and Characteristics

Veteran Participants: For the Specific Aim 2 Formative Evaluation of the initial implementation at the 6 sites, which will assess adaptation of the Blended model to the CBOC setting during the implementation phase at each site, approximately 24 Veteran patients will be enrolled to participate in qualitative interviews. For the Specific Aim 2 Effectiveness test, we propose to enroll approximately 750 Veterans who screen positive on routinely administered VA MH screens (e.g., depression, alcohol, PTSD) at the 6 study CBOCs, for 18 months beginning at the first implementation period and continuing until the last two sites have completed the implementation phase (see methods section). Only those patients receiving specialty MH treatment in the 6 months prior to recruitment; those with a diagnosis of substance dependence; and those with a psychotic disorder diagnosis (schizophrenia, bipolar disorder, other psychotic disorders) will be excluded. Patients who consent to participate will participate in an initial assessment of health status by telephone and a follow-up telephone assessment six months later.

For the exploratory third aim at the CBOCs, up to 40 total Veterans will be enrolled to participate in qualitative interviews about their HCV or HIV/mental health treatment experiences and preferences. Two subsets of Veterans will comprise the total sample for this aim:

1. 20 Veterans diagnosed with HCV.
2. 20 Veterans diagnosed with HIV and screen positive on a depression screen.

Provider Participants: For post-implementation interviews (Specific Aim 2 Formative Evaluation), the CBOC director, site champion, and any other relevant staff they recommend to us at each of the 6 study CBOCs will be recruited to participate in qualitative interviews. The telehealth MHPs involved in the study will also be interviewed.

Inclusion of Non-Veteran Participants: All patient participants will be Veterans. Because some of the provider and manager participants will not be Veterans, the study will request approval to recruit non-Veterans.

Sources of Materials

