Figure 2. We will harness recruitment efforts currently existing in the parent study and if we are unable to generate adequate sample size using this method, Veterans will be identified by their Patient Aligned Care Team provider. Through either method, Veterans will first be sent an opt-out letter. If Veterans do not call our research team within two weeks to opt out of the study, they will be called by our research team to assess interest and confirm eligibility in the study using a screening questionnaire. We are requesting a Waiver of Informed Consent for recruitment and a Waiver of Documentation of Informed Consent for participation. We will obtain verbal consent over the phone and document that we have obtained verbal consent in the research record. If Veterans are eligible and consent to participate, they will be scheduled with [name] for an interview via phone at their convenience.

Figure 2. Recruitment Flowchart for Exploratory Study (Aim #3)

Inclusion Criteria: All Veterans in the exploratory aim must identify with a race other than white--e.g, black, African American, or Latino. There are two subsets of inclusion criteria, one for each subsample within this exploratory study aim. (1) HCV: Veterans must have a chart diagnosis of HCV. (2) HIV. Veterans must have a chart diagnosis of HIV and screen positive for depression.

Data sources: There are two potential sources of data for this exploratory Aim #3:

- (1) Administrative Data also utilized for Specific Aim #2 (Effectiveness). Data will be collected on all patients at the study sites regardless of whether the patient was recruited and provided informed consent to participate in the primary data collection efforts associated with the trial. From this larger administrative dataset, Veterans diagnosed with either HCV or HIV will be recruited and sent opt-out letters, allowing them two weeks to opt out of the exploratory study.
- (2) Interview Data: This includes questions about HCV or HIV/depression treatment experiences, preferences, barriers, and facilitators; a demographics questionnaire.

Timeline: Recruitment will occur between July – September 30, 2016.

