Follow-up Interviews: We will contact participants with HCV who are enrolled for Aim 3 by telephone to assess whether they have initiated HCV treatment since the interview and if so, assess their reasons for doing so. These Veterans agreed at the end of the initial interview that they would allow our research team to contact them again, if needed. The phone call will last approximately 5-10 minutes and will follow a semi-structured script, allowing the interviewer (either [name] or the original research assistant who called the participant) to systematically ask questions while also exploring other themes Veterans highlight. The purpose of these follow-up interviews is to assess whether the initial interview itself (especially the education provided to Veteran participants about the new HCV treatment) served as a proxy or intervention for helping Veterans initiate HCV treatment. We may also ask Veterans to clarify or comment on any results from our analysis of their initial interviews—this “member checking” procedure is common in qualitative analysis to ensure valid data interpretation.

Analysis: [name] and other research staff will code the qualitative data using qualitative analytic techniques.

Measures Taken to Minimize/Avoid Bias, such as Randomization and Blinding:

We will use CDW data and an opt-out approach to recruit a representative sample of Veterans meeting the eligibility criteria for the exploratory aim. Because this is an exploratory aim, randomization and blinding is neither possible nor required for proper scientific rigor.

Expected Duration:

Participation for the formative evaluation interviews will be limited to one interaction for qualitative data collection. Participants in the effectiveness trial will be interviewed at the time of enrollment and 6 months thereafter, as described above. Participants in the exploratory aim will be interviewed at time of enrollment between July and September 30, 2016.

Stopping or Discontinuation Criteria for Individual Participants:

Participants are free to discontinue participation in interviews at any time. An individual’s participation will be discontinued if the participant appears to be experiencing severe distress related to the intervention or assessments.

Selection and Withdrawal of Participants:

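### The HCV follow-up calls can describe whether Veterans credit the interview, but they cannot show that it led to treatment starts

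*Combined protocol and SAP*

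**What the plan says.** Under Follow-up Interviews (Exploratory Study, Specific Aim 3) the purpose is given as follows: "The purpose of these follow-up interviews is to assess whether the initial interview itself", with emphasis on the education it gave about the new HCV treatment, "served as a proxy or intervention for helping Veterans initiate HCV treatment".

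The same subsection sets who is called and what is asked. "We will contact participants with HCV who are enrolled for Aim 3 by telephone" names the group, and the call is to "assess whether they have initiated HCV treatment since the interview and if so, assess their reasons for doing so". The call is short and semi-structured, may explore other themes, and may include member checking. The only analysis named for the aim is qualitative coding. The interval between interview and call is not stated.

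Population to be Studied sets the subsample at "20 Veterans diagnosed with HCV", and Study Design makes that a maximum. The Aim 3 inclusion criteria ask for a chart diagnosis of HCV and a race other than white. Neither those criteria nor Selection and Withdrawal of Participants removes Veterans already treated.

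On background, the HCV Treatment paragraph describes new, essentially curative antivirals within VA and adds: "VA continues to fund HCV treatment" and "Less than 30% of HCV+ Veterans have received treatment".

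**The concern.** Whether the interview acted as an intervention is a question about what would have happened without it. Everyone called had the interview, and the plan provides no uninterviewed group, earlier rate or external benchmark. With treatment available and funded, some Veterans would be expected to start anyway.

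Three features make the answers harder to read:

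- Veterans who heard the education and did not start are the natural counter-evidence, but the plan asks for reasons only from starters.
- A Veteran treated before the interview cannot start afterwards, so the number able to start is not defined.
- The caller may be the research assistant who made the first telephone contact, which may encourage a polite answer that credits the study.

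Study Design says Aim 3 will give preliminary data to the Office of Health Equity for treatment policy and later grants. If the calls were reported as showing that the interview worked, ordinary uptake could be carried forward as an effect. The protocol's Background holds earlier co-located care studies to this standard: it calls their findings hard to interpret for want of a control group.

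**Working it through.** The documents give no sample size, expected rate, alpha or power for these calls, so there is no figure to reproduce. The calculations below are illustrations; every start probability is an assumption.

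**1. What a count would show with no interview effect.** Input from the plan: n = 20 (maximum). Assumed: background start probability p of 5% to 30% over the unstated interval. Expected starts = 20p, and P(at least 3) = 1 − Σ C(20,x) pˣ(1−p)²⁰⁻ˣ for x = 0, 1, 2. At p = 0.10 this is 1 − (0.1216 + 0.2702 + 0.2852) = 0.323.

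| Assumed p | Expected starts | P(at least 3 starts) |
|---|---|---|
| 5% | 1 | 7.5% |
| 10% | 2 | 32% |
| 20% | 4 | 79% |
| 30% | 6 | 97% |

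A handful of starts is therefore either unusual or nearly certain without any interview effect, depending on a background rate that the plan does not collect.

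**2. Precision of the count.** Exact (Clopper-Pearson) 95% intervals are 1–32% for 2/20, 6–44% for 4/20 and 12–54% for 6/20.

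**3. Fewer Veterans may be able to start.** If the under-30% figure for HCV-positive Veterans in general applied to this subsample, at least 20 × (1 − 0.30) = 14 would be expected to be untreated. Whether it applies is an assumption. With 14 at risk, hypothetical counts of 3 and 5 give 21% (95% interval 5–51%) and 36% (13–65%). The under-30% figure is also the proportion ever treated. It is not a start rate over the follow-up window, so it cannot serve as the missing benchmark.

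**4. What a comparison group could and could not do.** Assume 20 interviewed and 20 uninterviewed Veterans and a two-sided 0.05 test of two proportions. Let p̄ be the mean of the two proportions and d their difference. Then z = [d√20 − 1.96√(2p̄(1−p̄))] / √(p₁(1−p₁) + p₂(1−p₂)), and power = Φ(z). For 10% vs 30%, z = (0.894 − 1.109)/0.548 = −0.39, so power is 35%.

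| Assumed contrast | Power at 20 per group | Needed per group for 80% power |
|---|---|---|
| 10% vs 30% | 35% | 62 |
| 20% vs 40% | 28% | 82 |
| 30% vs 50% | 25% | 93 |

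A comparison group of this size would give context for a count. It could not test the interview's effect.

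**The case against.** The strongest reply is that the calls are qualitative work in an aim declared exploratory. The plan computes no rate and proposes no test. It asks starters why they started, and asking people whether the interview prompted them is a recognised way to learn about perceived influence without a control group. This stands. A reader might infer that the stated purpose cannot be met at all. The documents do not support that: if the purpose is read as perceived influence, the calls can give weak, hypothesis-generating evidence on it.

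A reader might also infer that HCV treatment was being expanded during the follow-up window. The protocol documents new antivirals, continuing funding and low coverage. It documents no expansion in that period, and it stresses barriers to uptake. Some background starts are plausible, but their rate is unknown.

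Other parts of the reply also stand:

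- The calls ask about starts since the interview, and the first interview covers treatment experience, so the untreated denominator may be recoverable from data already collected.
- The Administrative Data section lists no antiviral or pharmacy records among its fields, so a comparison would need an added data request.
- Uninterviewed Veterans differ from those who did not opt out, consented and agreed to be called again.
- Names are removed from the text, so it cannot be confirmed whether the caller would be the person who conducted the interview.

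The reply does not rescue the causal wording. Recalled reasons from starters alone cannot show that those starts would not have happened anyway, and calling the aim exploratory does not change that.

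**Conclusion.** The concern holds in a limited form. As planned, the calls can describe whether Veterans who started treatment credit the interview or its education. They cannot show that the interview led to starts, because nobody uninterviewed is observed, non-starters are not asked for reasons, the group able to start is undefined, and no background rate is collected.

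The illustrated chance of at least 3 starts in 20 with no interview effect runs from 7.5% to 97% as the assumed background probability goes from 5% to 30%. Those probabilities, and the figure of 14 untreated, are assumptions. The conclusion does not depend on them; it follows from the absence of any contrast. Severity is low: this is a small add-on to an exploratory aim and does not touch Hypothesis 1 or 2.

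**What to change.** 1. Restate the purpose under Follow-up Interviews as describing the influence that Veterans report the interview and its education had on their treatment decisions, and drop the claim to assess whether the interview acted as an intervention.
2. Put the question about reasons to Veterans who did not start as well as to those who did.
3. Record HCV treatment status at the interview date and state when the call is made.
4. If any count of starts is reported, restrict it to Veterans untreated at interview. Show it descriptively beside starts over the same calendar window among untreated, uninterviewed, HCV-diagnosed minority Veterans at the six CBOCs. The Aim 3 Data sources paragraph already provides the population ("Data will be collected on all patients at the study sites regardless of whether the patient was recruited"), but antiviral records would have to be added to the administrative extract.

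Items 1 to 3 cost a reworded sentence, one more question in a short script, one recorded status and a stated interval. Item 4 costs one data request and a small table, and is needed only if a count is reported. Its downside is that the comparison is small, observational and affected by self-selection, so it should be labelled a benchmark and not a test.
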